8.3 Instructions for Patients

Patients are instructed to strictly follow the study visit schedule and to report all changes in condition to the investigative site.

8.4 Unscheduled Visits

Additional examinations may be performed as necessary to ensure the safety and well being of patients during the study period. Unscheduled visit eCRFs should be completed for each unscheduled visit. For all parameters not measured, “Not Done” should be indicated and the forms should be signed and dated as appropriate.

8.5 Compliance with Protocol

Patients who are inadvertently enrolled, despite significant deviation from protocol-specified inclusion/exclusion criteria, will be followed to monitor patient safety.

Patients will be scheduled for follow-up visits, and these should occur as close as possible to the day specified in the visit schedule.

At each visit after day 1, the investigator will ask patients if they have used any concomitant medications, and have had a procedure performed since the previous visit.

8.6 Early Discontinuation of Patients

Patients may voluntarily withdraw from the study at any time.

Notification of early patient discontinuation from the study and the reason for discontinuation will be made to Allergan and will be clearly documented on the appropriate eCRF.

8.7 Study Termination

The study may be stopped at his/her study site at any time by the site investigator. Allergan may stop the study (and/or the study site) for any reason with appropriate notification.

9. Adverse Events

Adverse events occurring during the study will be recorded on an adverse event eCRF. If adverse events occur, the first concern will be the safety of the study participants.

9.1 Definitions

9.1.1 Adverse Event

An adverse event is defined as any untoward medical occurrence in a patient or clinical investigation subject administered a pharmaceutical product and that does not necessarily have a causal relationship with this treatment. An adverse event can therefore be any unfavorable and unintended sign (including an abnormal laboratory finding), symptom, or disease temporally associated with the use of a medicinal (investigational) product, whether or not related to the medicinal (investigational) product. In addition, during the screening period, adverse events will be assessed regardless of the administration of a pharmaceutical product.

Adverse events will be assessed and documented, as appropriate, throughout the study (ie, after informed consent has been obtained). At each visit, the investigator will begin by querying for adverse events by asking each patient a general, nondirected question, such as “How have you been feeling since the last visit?” Directed questioning and examination will then be done as appropriate. All reported adverse events will be documented on the appropriate eCRF.

9.1.2 Serious Adverse Event

A serious adverse event is any adverse event occurring at any dose that results in any of the following outcomes: death, a life-threatening adverse event, inpatient hospitalization or prolongation of existing hospitalization, a persistent or significant disability/incapacity, or a congenital anomaly/birth defect. Important medical events that may not result in death, be life-threatening, or require hospitalization may be considered a serious adverse event when, based upon appropriate medical judgment, they may jeopardize the patient and may require medical or surgical intervention to prevent 1 of the outcomes listed in this definition. (See Section 9.3 for procedures for reporting a serious adverse event.)

Note: Allergan considers all cancer adverse events as serious adverse events. In addition, Allergan considers any abortion (spontaneous or nonspontaneous) as a serious adverse event.

9.1.3 Severity

A clinical determination will be made of the intensity of an adverse event. The severity assessment for a clinical adverse event should be completed using the following definitions as guidelines:

Mild	Awareness of sign or symptom, but easily tolerated
Moderate	Discomfort enough to cause interference with usual activity
Severe	Incapacitating with inability to work or do usual activity
Not applicable	In some cases, an adverse event may be an ‘all or nothing’ finding that cannot be graded

9.1.4 Relationship to Study Drug or Study Procedure

A determination will be made of the relationship (if any) between an adverse event and the study drug or study procedure, as applicable. A causal relationship is present if a

determination is made that there is a reasonable possibility that the adverse event may have been caused by the drug or study procedure.

9.2 Procedures for Reporting Adverse Events

Any adverse event should be recorded on the appropriate eCRF.

All adverse events that are drug-related and unexpected (not listed as treatment-related in the current Investigators Brochure) are to be reported to the governing Institutional Review Board/Independent Ethics Committee (IRB/IEC) as required by the IRB/IEC, local regulations, and the governing health authorities.

9.3 Procedures for Reporting a Serious Adverse Event

Any serious adverse event occurring during the study period (beginning with informed consent) and for at least 2 months after the last dose of study drug should be immediately reported to an Allergan representative listed on the Allergan personnel page and recorded on the appropriate eCRFs. All patients with a serious adverse event must be followed up, and the outcomes reported. The investigator should supply Allergan and the IRB/IEC with any additional requested information (eg, autopsy reports and terminal medical reports).

In the event of a serious adverse event, the investigator must:

1. Notify Allergan immediately by fax using the serious adverse event reporting forms (for serious adverse event fax number, see page 1 of the protocol). Emergency phone numbers and relevant Allergan personnel contacts are also on the front page of protocol.
2. Obtain and maintain in his/her files all pertinent medical records, information, and medical judgments from colleagues who assisted in the treatment and follow-up of the patient.
3. Provide Allergan with a complete, written case history (adverse event report form) that includes a statement as to whether the event was or was not related to the use of the investigational drug.
4. Promptly inform the governing IRB/IEC of the serious adverse event as required by the IRB/IEC, local regulations, and the governing health authorities.

9.4 Procedures for Unmasking of Study Medication

Investigators will be aware of the treatment assignment.

10. Administrative Items

This protocol is to be conducted in accordance with the applicable Good Clinical Practice (GCP) regulations and guidelines, eg, the International Conference on Harmonisation (ICH) Guideline on GCP.

10.1 Protection of Patients

10.1.1 Compliance with Informed Consent Regulations and Relevant Country Regulations

Written informed consent is to be obtained from each patient prior to enrollment into the study, and/or from the patient's legally authorized representative in accordance with local regulatory requirements.

There are special situations in which oral informed consent may be taken. Approval to utilize oral consent procedures and instructions on how to properly obtain oral informed consent must be obtained from Allergan personnel.

10.1.2 Compliance With IRB/IEC Regulations

This study is to be conducted in accordance with applicable IRB/IEC regulations. The investigator must obtain approval from a properly constituted IRB/IEC prior to initiating the study and re-approval or review at least annually. Allergan is to be notified immediately if the responsible IRB/IEC has been disqualified or if proceedings leading to disqualification have begun. Copies of all IRB/IEC correspondence with the investigator should be provided to Allergan.

10.1.3 Compliance With Good Clinical Practice

This protocol is to be conducted in accordance with the applicable local GCP regulations and guidelines.

10.1.4 Compliance With Electronic Records; Electronic Signatures Regulations

This study is to be conducted in compliance with the regulations on electronic records and electronic signature.

10.2 Changes to the Protocol

The investigator should not implement any deviation from or changes of the protocol without approval by Allergan and prior review and documented approval/favorable opinion from the IRB/IEC of a protocol amendment, except where necessary to eliminate immediate hazards to study patients, or when the changes involve only logistical or administrative aspects of the study (eg, change in monitors, change of telephone numbers).

10.3 Patient Confidentiality

A report of the results of this study may be published or sent to the appropriate health authorities in any country in which the study drug may ultimately be marketed, but the patient's name will not be disclosed in these documents. The patient's name may be disclosed to Allergan, the governing health authorities if they inspect the study records. Appropriate precautions will be taken to maintain confidentiality of medical records and personal information.

10.3.1 Patient Privacy

Documentation in accordance with the relevant local privacy requirements (where applicable) is to be obtained from each patient prior to enrollment into the study, and/or from the patient's legally authorized representative in accordance with the applicable privacy.

10.4 Documentation

10.4.1 Source Documents

Source documents may include a patient's medical records, hospital charts, clinic charts, the investigator's patient study files, as well as the results of diagnostic tests, such as x-rays, laboratory tests, and electrocardiograms. The investigator's copy of the eCRFs serves as part of the investigator's record of a patient's study-related data.

The following information should be entered into the patient's medical record:

- patient's name
- patient's contact information
- the date that the patient entered the study, patient number, and patient randomization (or medication kit) number
- the study title and/or the protocol number of the study and the name of Allergan
- the statement that informed consent has been obtained (including the date) prior to any study procedures being performed. A statement that privacy required documentation for this study has been obtained (including the date).
- dates of all patient visits
- medical history, including childbearing potential (if female), height, and weight
- ophthalmic history
- all concurrent medications (List all prescription and nonprescription medications being taken at the time of enrollment. At each subsequent visit, changes to the list of medications should be recorded.)
- vital signs (blood pressure and pulse rate)
- manifest refraction and visual acuity worksheets
- BCVA (source document information for these procedures must be captured and maintained in such a manner that the study personnel performing these examinations do not have access to the remaining study-related information or the source documents for any previous BCVA examinations)
- IOP measurements
- biomicroscopy results
- indirect ophthalmoscopy results
- FA duplicates, as well as backup copies of the electronic records if a digital system is used

- printouts of OCT, as well as backup copies of the electronic records
- occurrence and status of any adverse events
- procedure notes of the study treatment procedure should include the following information: date and time of the procedure, evaluation of the injection site, location of injection to the nearest clock hour, and complications, if any
- date the patient exited the study and a notation as to whether the patient completed the study or reason for discontinuation
- the results of laboratory tests performed by the site (eg, results of urine pregnancy tests)
- all concurrent procedures and concurrent medications (list all prescription and nonprescription medications being taken at the time of enrollment; at each subsequent visit, changes to the list of medications should be recorded)
- any study personnel with knowledge of treatment assignment who shares this information with study personnel with no knowledge of a patient's treatment assignment and/or shares this information with patients; the information shared is to be listed by parameter shared, whom the information was shared with, and the date it was shared

█ [REDACTED]

10.4.2 Electronic Case Report Form Completion

The investigator is responsible for ensuring that data are properly recorded on each patient's eCRFs and related documents. An investigator who has signed the protocol signature page should personally sign for the eCRFs (as indicated in the eCRFs) to ensure that the observations and findings are recorded on the eCRFs correctly and completely. The eCRFs are to be submitted to Allergan in a timely manner at the completion of the study, or as otherwise specified by Allergan.

10.4.3 Study Summary

An investigator's summary will be provided to Allergan within a short time after the completion of the study, or as designated by Allergan. A summary is also to be provided to the responsible IRB/IEC.

10.4.4 Retention of Documentation

All study-related correspondence, patient records, consent forms, patient privacy documentation, records of the distribution and use of all investigational products, and copies of eCRFs should be maintained on file.

For countries falling within the scope of the ICH guidelines, the Allergan-specific essential documents should be retained until at least 2 years after the last approval of a marketing application in an ICH region and until there are no pending or contemplated marketing applications in an ICH region or at least 2 years have elapsed since the formal discontinuation of clinical development of the investigational product. These documents should be retained for a longer period, however, if required by the applicable regulatory requirements or if needed by Allergan.

In addition, for countries not falling within the scope of the ICH guidelines, local regulatory requirements should be followed regarding the retention of clinical study documentation.

Allergan requires that it be notified in writing if the investigator wishes to relinquish ownership of the data so that mutually agreed-upon arrangements can be made for transfer of ownership to a suitably qualified, responsible person.

10.5 Labeling, Packaging, and Return or Disposal of Study Medications/Treatments

10.5.1 Labeling/Packaging

The study medications will be packaged, labeled, and supplied by Allergan. All test articles will be identified as an investigational compound and will be labeled with the protocol study number and medication kit number. The label will also specify the storage conditions and state that the study medication is limited to investigational use.

10.5.2 Clinical Supply Inventory

The investigator must keep an accurate accounting of the number of investigational units received from Allergan, dispensed to the patients, the number of units returned to the investigator by the patient, and the number of units returned to Allergan during and at the completion of the study. A detailed inventory must be completed for the study medication. The study medication must be dispensed only by an appropriately qualified person to patients

700 µg DEX PS DDS

in the study. The medication is to be used in accordance with the protocol by patients who are under the direct supervision of an investigator.

10.5.3 Return or Disposal of Study Medications/Treatments and /or Supplies

All clinical study medications/treatments and/or supplies will be returned to Allergan or Allergan designee for destruction.

10.6 Monitoring by Allergan

A representative of Allergan will monitor the study on a periodic basis. The determination of the extent and nature of monitoring will be based on considerations such as the objective, purpose, design, complexity, blinding, size, and endpoints of the study.

Authorized representatives of Allergan or regulatory authority representatives will conduct on-site visits to review, audit, and copy study-related documents. These representatives will meet with the investigator(s) and appropriate staff at mutually convenient times to discuss study-related data and questions.

10.7 Handling of Biological Specimens

Samples of blood and urine for evaluation of hematology, biochemistry, and urinalysis will be analyzed at a facility meeting Good Laboratory Practice requirements and/or a validated method of quality assurance.

Pharmacokinetic blood samples will be analyzed by a bioanalytical laboratory that meets Good Laboratory Practice requirements. Details about collection and handling of the pharmacokinetic blood samples are provided in the Procedure Manual.

10.8 Publications

Allergan as the sponsor, has proprietary interest in this study. Authorship and manuscript composition will reflect joint cooperation between multiple investigators and sites and Allergan personnel. Authorship will be established prior to the writing of the manuscript. As this study involves multiple centers, no individual publications will be allowed prior to completion of the final report of the multicenter study except as agreed with Allergan.

12.1 Examination Procedures, Tests, Equipment, and Techniques

[REDACTED]

[REDACTED]

[REDACTED]

[REDACTED]

[REDACTED]

[REDACTED]

[REDACTED]

[REDACTED]

[REDACTED]

[REDACTED]

[REDACTED]

12.1.2 Pregnancy Test

Females of childbearing potential will have urine pregnancy tests performed. A female is considered to be of childbearing potential unless she is postmenopausal and without menses for 12 months or without a uterus and/or both ovaries. Pregnancy test kits will be administered according to the instructions provided with the tests. A negative pregnancy test result (required for female patients of childbearing potential only) must be obtained at screening and at the day 1 visit before study drug injection. An additional test is required at the month 12/exit visit.

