4.5.2 Acceptable Contraceptive Methods

Women of childbearing potential must use reliable contraception. The investigator and each patient will determine the appropriate method of contraception for the patient during the participation in the study.

If a female of childbearing potential becomes pregnant during the study, the investigator will notify Allergan immediately after the pregnancy is confirmed, and the patient will be exited from the study after appropriate safety follow up. The investigator will (1) notify the patient's physician that the patient was being treated with an investigational drug (if applicable), 700 µg DEX PS DDS, and (2) follow the progress of the pregnancy. The investigator should discontinue study treatment, document the outcome of the pregnancy, and provide a copy of the documentation to Allergan.

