5.7 Treatment Regimen and Dosing

5.7.1 DEX PS DDS

Patients assigned to the DEX PS DDS treatment group will receive 700 µg dexamethasone in a solid polymer delivery system at day 1, months 5, and 10.

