5.9 Study Drug Administration

5.9.1 Peri-operative Anti-infective Treatment

At the visit preceding each study drug administration, the patient will be given antibiotic ophthalmic solution (as applicable according to local practice) and instructed to instill a drop in the SE 4 times per day (QID) for 3 days prior to the study treatment procedure and up to QID (depending on the time of the study treatment procedure) on the day of the procedure, and QID for 3 days postoperatively. Patients should be instructed not to wear contact lenses while using antibiotics. See the Procedure Manual for further details.

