7.2 Collection and Derivation of Primary and Secondary Efficacy Assessments

BCVA measured in the SE using the ETDRS method will be the primary efficacy assessment. For each patient, BCVA data will be collected for both the study and nonstudy eyes at the

screening, day 1/randomization day (prior to the study treatment), and months 1, 2, 3, 5, 6, 7, 9, 10, and 12/exit (or early exit) visits. Analysis of BCVA obtained from the SE will be performed for efficacy. BCVA data from the nonstudy eye will be used only for safety evaluations.

VA will be recorded on the CRF as the number of letters correctly read. For a given eye, the 4-meter distance (standard) of VA will be tested first. If the patient correctly reads at least 20 letters at 4 meters, the VA score will be set as the sum of 30, and the number of letters read correctly. If the patient correctly reads less than 20 letters at 4 meters, the VA will be measured again at 1 meter. The VA score will be set to the number of letters read correctly at 1 meter plus the number of letters read correctly at 4 meters.

BCVA measured at the randomization visit on day 1 prior to the study treatment will be considered as baseline for change from baseline. BCVA data measured at the screening visit will be used for baseline only in the absence of BCVA data at the randomization visit on day 1.

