7.5 Interim Analyses

No interim analysis is planned for this study.

8. Study Visit Schedule and Procedures

The total duration of study participation for each patient is approximately 12.5 months, including screening and randomization/retreatment period. Patients will attend the following

11 visits: screening visit, randomization visit, 8 assessment/retreatment visits, and study exit visit. Please see Table 1 and Figure 1 for a schematic of the schedule of visits and procedures.

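### In the readable text, a negative pregnancy test is required before the first implant but not before the month 5 and month 10 implants, about 149 and 299 days after the last required test

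*Protocol*

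**What the plan says.** Protocol section 12.1.2 applies to women of childbearing potential. A negative urine test "must be obtained at screening and at the day 1 visit before study drug injection". The only later test it names is at the end of the study: "An additional test is required at the month 12/exit visit".

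Section 5.7.1 gives the implant arm 700 µg dexamethasone "in a solid polymer delivery system at day 1, months 5, and 10", so two of the three implants come after day 1.

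Section 4.5.2 requires reliable contraception and leaves the method to the investigator and the patient. If a pregnancy is confirmed, the sponsor is notified and the patient leaves the study after safety follow-up. It adds: "The investigator should discontinue study treatment, document the outcome of the pregnancy". It sets no test before re-injection.

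Section 9.1.1 opens each visit with a general, undirected question about how the patient has been, after which "Directed questioning and examination will then be done as appropriate".

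Section 8 refers to a full schedule: "Please see Table 1 and Figure 1 for a schematic of the schedule of visits and procedures". That table is not in the readable text, and the visit-by-visit procedures that follow section 8.1.2 are blacked out.

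**The concern.** The plan treats pregnancy as a reason not to give the implant. It tests before the first one and stops treatment if a pregnancy is confirmed. The same reasoning applies to the second and third implants, yet section 12.1.2 attaches no test to them. An early pregnancy that the patient has not noticed would not trigger the stopping rule, because nothing scheduled in the readable text would confirm it before re-dosing. The month 12/exit test comes after the last scheduled implant, when the dose can no longer be withheld. What is at stake is avoidable fetal exposure to a corticosteroid implant that releases drug gradually. No efficacy estimate or error rate depends on this.

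**Working it through.** The plan states no figure to reproduce. The check sets the test schedule against the dosing schedule and counts days.

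**Inputs**
- Required tests: screening, day 1 before injection, month 12/exit (protocol 12.1.2).
- Implants: day 1, month 5, month 10 (protocol 5.7.1).
- Target days and analysis windows (SAP Table 2-1): month 5 is day 150, window 121 to 165; month 10 is day 300, window 286 to 330; month 12 is day 360.
- The first treatment is study day 1 (SAP 2.3), so elapsed days = study day − 1.
- Enrolment of about 356, randomised 1:1, with at least 151 completers per arm (protocol 4.1 and 5.5).

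**Time from the last required test to each implant**

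| Implant | At target day | Across the analysis window |
|---|---|---|
| Day 1 | 0 (tested the same day) | – |
| Month 5 | 150 − 1 = 149 days | 121 − 1 = 120 to 165 − 1 = 164 days |
| Month 10 | 300 − 1 = 299 days | 286 − 1 = 285 to 330 − 1 = 329 days |

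If the table's target days are read as days elapsed since day 1, the gaps are 150 and 300 days. The next required test falls 360 − 300 = 60 days after the month 10 implant.

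**Number of women concerned**

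The documents do not give the share of childbearing potential. A range of 2% to 15% is assumed here. The implant arm has 356 / 2 = 178 patients.

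| Base | Women at 2% | Women at 15% | Repeat implants (× 2) |
|---|---|---|---|
| 178 enrolled | 3.6 | 26.7 | about 7 to 53 |
| 151 completers | 3.0 | 22.7 | about 6 to 45 |

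The enrolled row is an upper bound, since some patients will leave or move to escape therapy before receiving both repeat implants.

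**Opportunities to add a test**

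After day 1, visits with visual acuity testing take place at "months 1, 2, 3, 5, 6, 7, 9, 10, and 12/exit (or early exit) visits". Both repeat-dosing visits are in that list. Section 6.5 already supplies pregnancy test kits, and section 10.4.1 gives urine pregnancy tests as an example of a test performed by the site.

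**The case against.** The strongest objection is that the absence cannot be confirmed. Table 1 and the visit procedures, where a month 5 or month 10 test would normally be listed, are hidden, and redacted text does not count as missing from the plan. Section 12.1.2 sits in an attachment on techniques and could be read as a minimum. This stands as a limit on the claim, which covers the readable text only. But section 12.1.2 is not redacted, and by naming specific visits and a single additional test it reads as a complete list. If the hidden schedule adds tests, the section still needs to agree with it.

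Second, safeguards exist: mandatory contraception, a question at every visit (months 5 and 10 included), a stopping rule, and freedom to run an ad hoc test. These lower the risk, and the number of exposures actually prevented is likely to be small. They do not replace a test, because each depends on contraception working, on the patient's own awareness, or on someone's decision to check.

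Third, some of the sizing is soft. The 2% to 15% share is an assumption. The SAP windows assign measurements to analysis visits and do not limit when implants are given. SAP 2.3 reports that a product recall delayed some implants to month 12. The target-day gaps do not depend on the assumed share, and delayed doses are a further reason to tie the test to the implant and not to a fixed visit.

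Fourth, section 5.9.1 ties a pre-dose step to every dose ("At the visit preceding each study drug administration, the patient will be given antibiotic ophthalmic solution"), but that step addresses infection. It shows only that such wording is practicable, not how often to test for pregnancy.

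Finally, the recall note shows the trial was well advanced when the SAP was written, so an amendment at that stage would have helped few participants.

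**Conclusion.** The concern holds for the readable text. A site that follows section 12.1.2 as written may give the second and third implants with no pregnancy test since day 1, about 149 and 299 days earlier at the target visits. Under the assumed 2% to 15% share, about 4 to 27 women of 178 enrolled, or 3 to 23 of 151 completers, would be affected. The number of pregnancies actually exposed is probably low, and the documents do not allow it to be estimated. It is a modest participant-safety improvement that should be made because it costs so little. Confidence is medium because the hidden schedule may already contain the tests; in that case the point reduces to making section 12.1.2 consistent with it.

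**What to change.** Amend section 12.1.2 to require, for women of childbearing potential in the implant arm, a negative urine pregnancy test before every implant (day 1, month 5, month 10 and any delayed dose), and keep the screening and exit tests. Bring Table 1 and the visit procedures into line if they do not already say this. The cost is one sentence of amendment text and two extra urine tests per woman, taking a few minutes at visits that already occur, with kits of a type already supplied.
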